#### 3.4.2.11 End-of-Study Questionnaire at Week 28/Follow Up

Descriptive summary statistics on the values will be presented.

# 3.4.3 Subgroups

SNOT-22 total score and 3CS will be descriptively summarized for the Efficacy Analysis Set by nasal polyp status (with nasal polyp vs without) for Part 2 subjects.

#### 3.5 Pharmacokinetic Assessment

## 3.5.1 Sample Collections for Pharmacokinetic Analysis

PK blood samples for assessment of plasma mometasone furoate concentrations will be collected from all subjects on 9 occasions as specified:

- Day 1 pre-procedure
- 1 hour (±10 minutes) post procedure on Day 1
- Day 2 or 3
- Day 5 or 8
- Week 4
- Week 12
- Week 16 or 20
- Week 24, and
- Week 25/Follow Up

At Day 1 visit, the blood samples for plasma PK analysis will be collected before the LYR-220 administration procedure and 1 hour (±10 minutes) after the procedure. At the Week 24 visit, the blood sample will be collected before the LYR-220 removal procedure. Blood samples may be collected at any time of the day during all the other scheduled study visits.

#### 3.5.2 Handling Missing or Below the Lower Limit of Quantification Data

For PK concentration data, if the actual sampling time is missing, but a valid concentration value has been measured, the concentration value will be flagged, and the scheduled time point may be used for the calculation of PK parameters.

In cases of missing pre-dose concentrations for each treatment, the missing components may be assumed as zero. For the other cases, the missing data will not be imputed.

For the individual concentration and PK parameter calculation of each treatment, the following rules will be applied:

- If one or more BLQ values occur before the first measurable concentration, they will be assigned a value of zero.
- If BLQ values occur between measurable concentrations in a profile, the BLQ should be omitted (set to missing).
- If BLQ values occur after the last measurable concentration in a profile, the BLQ should be omitted (set to missing).

For the concentration summary and mean concentration plot preparation of each treatment, the following rules will be applied:

- Mean concentration at any individual time point will only be calculated if at least half of the subjects have valid values (i.e., quantifiable and not missing) at this time point for each treatment.
- In cases where a mean value is not calculated due to the above criterion not being met, the value will be set to missing.
- · BLQ values will be set to zero.

#### 3.5.3 Pharmacokinetic Concentration

Individual plasma concentrations of mometasone furoate will be summarized by treatment at each nominal time point for the PK Population descriptively. Individual plasma concentrations will also be listed for the PK Population. Listing of nominal times post dose and actual times will be provided. Deviations from the nominal times per protocol will be given in a separate listing. In listings, concentrations below the lower limit of quantification (LLOQ) will be reported as "<LLOQ", where LLOQ will be the actual value of LLOQ (to be determined).

Individual plasma concentration will be plotted by treatment on a linear and semi-log scale against actual sampling time points relative to dosing time. Mean (±SD) concentration will be plotted on a linear and semi-logarithmic scale against nominal time points by treatment, when available. LLOQ will be plotted as a reference line in both instances.

Actual sampling times that are outside the sampling time windows may be excluded from concentration summary and mean concentration plotting but will still be used in the calculations of PK parameters and individual concentration plotting.

A descriptive statistics summary of concentrations by LYR-220 design and actual PK sampling time, including number (n), mean, geometric mean, SD, coefficient of variation (CV), median, minimum, maximum, and the number of concentrations ≥LLOQ. The "<LLOQ" values will be set to zero based on Beal's method M7.

#### 3.5.4 Pharmacokinetic Parameters

The following plasma PK parameters of mometasone furoate will be determined using non-compartmental methods as appropriate:

Parameters	Description
C max	Maximum plasma concentration; determined directly from the concentration time profile; if the maximum plasma concentration occurs at more than one time point, $C_{\text{max}}$ is defined as the first maximum value

T max	Time to $C_{\text{max}}$ ; If the maximum value occurs at more than one time point, $T_{\text{max}}$ is defined as the first time point with this value.
C last	Observed plasma concentration corresponding to $T_{\text{last}}$ where $T_{\text{last}}$ is the time of last measurable observed concentration
AUC 0-last	Area under the plasma concentration vs time curve (AUC) from predose (time 0) to the time of the last quantifiable plasma concentration (C last )
AUC 0-12h	Area under the plasma concentration vs time curve (AUC) from predose (time 0) to 12 hours post dose
AUC 12havg	Calculated as AUC 0-last /T last *12 h

Actual collection times will be used in PK parameter calculations. The Linear-Log Trapezoidal method (equivalent to the Linear Up/Log Down option in WinNonlin) will be used in the computation of all AUC values.

No PK parameters will be calculated for subjects with 2 or fewer detectable concentrations in their PK profile.

PK parameters will be summarized descriptively as follows: n, arithmetic mean, standard deviation, geometric mean, geometric standard deviation, coefficient of variation (CV%), geometric CV% (calculated as: gCV% =SQRT(es²-1)\*100; where s is the standard deviation of the log-transformed values), minimum, maximum and median. Tmax will include median, minimum and maximum. No descriptive statistics will be determined when fewer than three individual PK parameters are available.

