- 1 hour (±10 min) post procedure on Day 1
- Day 2 or 3*
- Day 5 or 8*
- Week 4
- Week 12

- Week 16 or 20*
- Week 24/EOT
- Week 25

[*Note: Subjects will be asked to come to the clinic on either one of the 2 visit options.]

Enrolled subjects will be asked to complete a daily ePRO questionnaire to assess the severity of the 4 cardinal symptoms (CS) of CRS including nasal blockage/obstruction/congestion, facial pain/pressure, anterior/posterior nasal discharge, and loss of smell. In addition, the ePRO will capture use of daily saline irrigation by the subjects. Subjects will also complete 2 validated CRS-specific quality of life questionnaires, the SNOT-22 and CRS-PRO, at Screening, on Day 1 before treatment, and at Weeks 2, 4, 6, 8, 12, 16, and 20, at Week 24 before matrix removal, and at Week 28/EOS. CRS-PRO will also be assessed at Day 8 and Week 3. The PGIS will be assessed at Day 1 and at Weeks 8, 16, and 24/EOT. The PGIC will be assessed at Week 24/EOT. At Week 28/EOS visit, an End-of-Study questionnaire will be administered.

Ethmoid cavity opacification will be assessed by CT scans obtained during Screening (or using a historical CT scan taken within 3 months of Screening) and at Week 25 visit, unless medically contraindicated. Subjects will be instructed to stop use of saline rinse approximately 24 hours prior to the scheduled sinus CT. Daily saline irrigation should then continue following the sinus CT. If a subject is experiencing or recovering from a cold, acute exacerbation of nasal allergy, or upper respiratory tract infection at Week 25 visit, the CT assessment should be performed 4 weeks after resolution of the adverse event. If a subject early terminates from the study or requires SCS or sinonasal surgery as rescue treatment during the study, all attempts should be made to perform the follow-up CT before the subject receives the rescue treatment.

Concomitant Medications: Prohibited, Permitted, and Rescue

Subjects participating in the study are free to use any appropriate concomitant medications, if medically warranted per treating physician's discretion. However, a standardized concomitant medications regimen is recommended during the run-in and treatment stages to avoid confounding the safety, pharmacokinetic, and efficacy assessments of LYR-220.

Prohibited Concomitant Medications:

Use of the following medications is prohibited for the duration of the study:

- Any drug or product containing mometasone furoate (MF).

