Phone follow-up to collect any potential AEs and use of concomitant medications/procedures. a:

IOP assessment only. ġ.

- Informed consent to be obtained before any study-related assessments occur. ö
- Occurs before the LYR-220/sham insertion on Day 1 or removal procedures at Week 24. ų:
- Complete a serum pregnancy test at initial Screening visit and a urine pregnancy test in clinic at all subsequent visits during the treatment stage for female subjects of childbearing potential. ö
 - investigators must document their review of each laboratory report.
- Subjects return to clinic for PK assessment at only 1 of 2 timepoints at Visits 3 and 4. Subjects return to clinic for Visit 7 PK assessment either at Week 16 or Week 20; a telephone follow-up will be performed the week the subject is not returning for a PK draw. ii ii
 - Subjects will start daily saline irrigation during run-in period. н. Б
- Nasal safety assessments of ethmoid cavity including epistaxis, mucosal injury, and any other adverse findings will be performed on Day 1 (before LYR-220 insertion) and at Week 4, 12, 24/EOT, and 25 visits.
 - Daily (between 06:00.00AM and 11:59:59AM) cardinal CRS symptoms, to be recorded by the subject on ePRO questionnaire beginning at least 14 days preceding or on Day 1 visit (prior to randomization). ·--
 - All adverse events shall be reported after subject signs informed consent.
 - A physical examination of the head, eyes, ears, nose, and throat (HEENT). ы ні ні кі
 - To be performed within 5-9 days after removal procedure.
- If a subject is experiencing or recovering from a cold, acute exacerbation of nasal allergy, or upper respiratory tract infection at the Week 25/EOS visit, the CT assessment should be performed 4 weeks after resolution of the adverse event.
 - A blood sample for PK assessment should be collected 1 hour (±10 minutes) after bilateral LYR-220 insertion.
 - Week 28/EOS follow-up may be performed either as a telephone follow-up or an in-clinic visit (if subjects need to return a study supplied ePRO device).
 - It is recommended that the PGIS be completed after the 4CS questionnaire. The PGIS should be completed before the PGIC.
 - SNOT-22 to be recorded by the subject based on a recall period of 2 weeks (14 days) prior to visit.
 - CRS-PRO to be recorded by the subject based on a recall period of 7 days prior to the visit.

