9.7.2 Pharmacokinetic Parameters

If plasma MF levels are detectable, PK parameters of MF will be estimated using a standard noncompartmental PK approach based on individual plasma concentration-time data. Actual PK sampling times will be used in the derivation of PK parameters. Maximum concentration (C_{max}) and time to reach maximum concentration (T_{max}) will be taken directly from the observed data.

Total drug exposure up to the last measured concentration (AUC_{0-last}) and the 12-hour average drug exposure (AUC_{0-12h average}) will be calculated from the plasma concentrations versus time profiles. Descriptive statistics of these parameters will be presented by treatment group.

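### AUC0-12h in SAP 3.5.4 is interpolated for 11 of its 12 hours, so its value depends on whether the next sample fell on Day 2 or Day 3

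*SAP*

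**What the plan says.** SAP 3.5.4 lists Cmax, Tmax, Clast, AUC0-last, AUC0-12h and AUC12havg. AUC0-12h is defined as "Area under the plasma concentration vs time curve (AUC) from predose (time 0) to 12 hours post dose". AUC12havg is a different quantity: AUC0-last divided by Tlast, times 12 h. All areas use the linear-up/log-down trapezoid and actual collection times.

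SAP 3.5.1 has PK blood "collected from all subjects on 9 occasions as specified". On Day 1 the samples are "collected before the LYR-220 administration procedure and 1 hour (±10 minutes) after the procedure". The next is on Day 2 or Day 3, then Day 5 or 8, then Week 4 onwards. The Protocol 8.1 schedule notes confirm that these are alternatives: "Subjects return to clinic for PK assessment at only 1 of 2 timepoints at Visits 3 and 4". The Protocol synopsis puts it this way: "Subjects will be asked to come to the clinic on either one of the 2 visit options". Clock time after Day 1 is open, apart from the Week 24 sample preceding removal: "Blood samples may be collected at any time of the day during all the other scheduled study visits".

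Protocol 9.7.2 names Cmax, Tmax, AUC0-last and the "12-hour average drug exposure". It does not list a separate area from 0 to 12 hours. SAP section 5 states that nothing changes from the protocol-specified analyses.

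**The concern.** No sample is scheduled between 1 hour and Day 2 or 3, so nobody has an observed concentration at or near 12 hours. The SAP gives no specific rule for obtaining that value. By default it comes from the trapezoid drawn between the 1-hour sample and the next one, and the length of that segment differs by visit option. Two subjects with the same exposure could then be given different AUC0-12h values because one attended on Day 2 and the other on Day 3.

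SAP 3.5.4 summarises parameters without separating the two options. The mean, SD and CV% of AUC0-12h would therefore mix sampling design with drug exposure. A reader of the study report would see a figure that looks like measured early systemic exposure but is almost entirely interpolated. Its name is also close to that of AUC12havg, which is built quite differently.

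**Working it through.** The documents state no value of AUC0-12h, so there is no figure to reproduce. The check applies the SAP's own rule to the scheduled times.

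**Inputs from the documents.** Samples at pre-procedure (time 0) and "1 hour (±10 minutes) post procedure on Day 1", then Day 2 or Day 3 (SAP 3.5.1); linear-up/log-down rule (SAP 3.5.4); mometasone half-life 5.8 h (Protocol 4.1.1).

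**Assumptions.** Next sample at t2 = 24 h (Day 2) or 48 h (Day 3); pre-dose concentration 0; concentrations in arbitrary units.

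**Unsampled share.** (12 − 1)/12 = 11/12 = 92% of the window.

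**Formulas.** C1 is the 1-hour value and C2 the value at t2.

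- Rising or flat: C12 = C1 + (C2 − C1) × 11/(t2 − 1); AUC0-12h = C1/2 + 11 × (C1 + C12)/2.
- Falling: λ = ln(C1/C2)/(t2 − 1); C12 = C1 × exp(−11λ); AUC0-12h = C1/2 + (C1 − C12)/λ.

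**Same true curve, sampled on either day.** This is the cleaner test, because only the sampling changes.

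*Rise to a plateau of 10 with half-time 6 h.* C(1) = 1.091, C(24) = 9.375, C(48) = 9.961.

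- Day 2: C12 = 1.091 + 8.284 × 11/23 = 5.053; area = 0.55 + 33.79 = 34.3.
- Day 3: C12 = 1.091 + 8.870 × 11/47 = 3.167; area = 0.55 + 23.42 = 24.0.
- True area = 55.1. The computed values are 38% and 56% too low, and the Day 3/Day 2 ratio is 0.70. With half-times of 3, 12, 24 and 48 h the ratio is 0.76, 0.72, 0.80 and 0.88.

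*Decline from 100 at 1 h to a plateau of 10 with half-life 5.8 h.* C(24) = 15.76, C(48) = 10.33.

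- Day 2: λ = ln(100/15.76)/23 = 0.0803; C12 = 41.3; area = 50 + 730.4 = 780.4.
- Day 3: λ = ln(100/10.33)/47 = 0.0483; C12 = 58.8; area = 50 + 853.3 = 903.3.
- True area = 710.8, with the first hour taken as the same linear segment. The computed values are 10% and 27% too high, and the ratio is 1.16.

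*Decline with no plateau (exactly mono-exponential).* 662.0 on both days, equal to the true area, because log interpolation is then exact.

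**Same two observed values, only the day changed.**

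| C at 1 h | C at next sample | Day 2 | Day 3 | Day 3/Day 2 |
|---|---|---|---|---|
| 0 | 10 | 26.3 | 12.9 | 0.49 |
| 2 | 10 | 44.0 | 33.3 | 0.76 |
| 5 | 10 | 70.7 | 63.9 | 0.90 |
| 10 | 10 | 115.0 | 115.0 | 1.00 |
| 20 | 10 | 197.3 | 213.1 | 1.08 |
| 50 | 10 | 408.6 | 483.3 | 1.18 |
| 100 | 10 | 716.8 | 900.4 | 1.26 |

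In these cases the sampled first hour supplies 0 to 7% of the computed area.

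**Two further sources of movement.** If open clock times put the Day 2 sample anywhere from 18 to 30 h (an assumed range), the 2-then-10 case runs from 51.5 to 39.7. SAP 3.5.2 also omits a below-limit value lying between measurable ones. A below-limit Day 2/3 sample then stretches the segment to Day 5 or 8 (nominally 96 or 168 h), and the same case gives 28.1 or 25.9.

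**The case against.** The strongest reply is that little depends on this parameter. The PK endpoint in SAP 2.3.4 is the plasma concentrations. AUC0-12h has no test, threshold or decision attached. Individual concentrations are listed and plotted with actual times, so the gap is visible. That stands, and it is why the point is minor. A reader might infer that the PK objective is compromised; the documents do not support that.

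A reader might also infer that AUC0-12h will be set against a twice-daily inhaled reference. No such comparison is planned. The passage in Protocol section 11 is background on the predecessor product, LYR-210, in surgically naive patients. Nor do the documents say that subjects choose their visit day; who decides is not stated, and the arithmetic does not need it.

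It would be tempting to lead with the roughly two-fold gap in the first table row. That is the extreme of the cases tried, with nothing measurable at 1 hour. Holding the observed values fixed while moving the day generally implies two different true curves, so part of the gap could be real. The same-curve results are the fairer guide.

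SAP 3.5.4 does allow parameters to be determined where appropriate, and bars them for subjects with two or fewer detectable concentrations. That gives room to drop AUC0-12h but no rule for doing so. The count of detectable values also says nothing about whether any lie near 12 hours.

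Finally, AUC0-last and AUC12havg also depend on the visit options and on Tlast. True, but they use the whole measurable profile. Over 24 weeks (24 × 168 = 4,032 h), a 12-hour window is about 0.3% of the time.

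**Conclusion.** The point holds as a minor one. The sampling gap is confirmed in both documents, and under the SAP's own rule AUC0-12h varies with the visit day unless the profile is flat or exactly mono-exponential. For the two worked plateau curves the Day 3/Day 2 ratio is 0.70 and 1.16, and neither day recovers the true area. With observed values held fixed it spans about 0.49 to 1.26. These sizes rest on assumed concentrations and nominal times of 24 and 48 h; the real size cannot be known from the documents. The consequence is confined to one descriptive parameter that Protocol 9.7.2 does not request. The concentration endpoint, Cmax and Tmax do not use the interpolated value.

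**What to change.** Delete AUC0-12h from SAP 3.5.4 and report AUC0-last and AUC12havg, the two exposure measures that Protocol 9.7.2 names.

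If the sponsor prefers to keep it, label it as interpolated, state how the 12-hour concentration is derived, report it separately for subjects sampled on Day 2 and on Day 3, and record it in SAP section 5 as an addition to the protocol.

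The cost is a documented SAP change and, with deletion, one descriptive parameter fewer. No visit, sample or subject number changes. The SAP is already a signed version 1.0, and its section 4.2 treats changes affecting the analysis after the primary lock as post hoc, so a later change should be labelled that way.

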## 3.6 Safety Assessment

Safety data will be summarized by actual treatment received based on the Safety Analysis Set. Safety data will be listed by site and subject.

#### 3.6.1 Adverse Events (AEs)

An AE is any untoward medical occurrence (signs, symptoms, clinically significant abnormal laboratory findings) in a subject regardless of relationship to the investigational product or procedure.

All AEs will be coded to system organ class and preferred term using the MedDRA version 24.1 (or later version).

TEAEs are defined as AEs that start after the initiation of study treatment administration but no later than 31 days (>31 days) after discontinuation of study treatment.

Treatment-emergent serious adverse events (TESAEs) are defined as SAEs that start after the initiation of study treatment administration but no later than 31 days (>31 days) after discontinuation of study treatment.

An overview of AEs will be provided including counts and percentages of subjects (and event counts) with the following:

- Any TEAEs (overall and by maximum severity)
- Any product related TEAEs (overall and by maximum severity)
- Any study procedure related TEAEs (overall and by maximum severity)
- Any treatment-emergent serious AEs (TESAEs)
- Any TEAEs leading to discontinuation of study product
- Any AEs leading to death
- Any TEAEs related to COVID-19

Counts and percentages of subjects (and event counts) will also be presented by primary system organ class and preferred term for each of the categories in the overview. Listings will be presented specifically for product related TESAEs/TEAEs, and TEAEs leading to discontinuation of study drug.

#### 3.6.2 Clinical Laboratory Tests

Samples for hematology and blood chemistry assessments will be obtained during Screening and Week 25/Follow Up visits, and processed by Reference Labs, the central laboratory. A list of laboratory tests to be performed is included in Appendix C.

Descriptive statistics for values will be presented.

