1. SYNOPSIS

Sponsor	Lyra Therapeutics, Inc.	
	[name]	
	[name]	
Protocol Title	BEACON: A Phase II, Patient-blinded, Two-part,	
	Randomized, Parallel-group Trial to Evaluate the Safety,	
	Tolerability, Pharmacokinetics, and Efficacy of LYR-220 in	
	Chronic Rhinosinusitis (CRS) Patients Who Have Had a	
	Prior Ethmoidectomy	
Protocol Number	LYR-220-2021-001	
Phase of Development	Phase II	
Investigational Product	LYR-220-32 System (7500 µg) and LYR-220-16 System	
	(7500 µg)	
Active Ingredient	Mometasone furoate (MF)	
Trial Location	Worldwide	
Number of Sites	Up to 25 sites	
Study Population	Adult CRS patients who have had a prior bilateral total	
	ethmoidectomy	
Estimated Number of Subjects	Approximately 50 subjects	
Study Endpoints	Study Endpoints	
Primary		
- Product-related unexpected serious adverse events		
Pharmacokinetics		
- Plasma MF concentrations at 1	hour post study treatment administration and at Days 2 or 3,	
Days 5 or 8, and Weeks 4, 12, 16 or 20, 24, and 25		
Secondary – Safety		
- Treatment-emergent adverse events (TEAEs) and serious adverse events (TESAEs) through		
Week 28		
- Clinically significant abnormal laboratory values (hematology and chemistry) through Week 25		
- Newly identified or worsened endoscopic findings (epistaxis and mucosal injury) in ethmoid		
cavity through Week 25		

- Clinically significant increase of IOP through Week 25

A clinically significant increase of IOP is defined as IOP in 1 or both eyes >23 mm Hg or an increase of IOP from Baseline in 1 or both eyes ≥ 10 mm Hg.

- Newly identified or worsened cataract in 1 or both eyes by slit-lamp examination through Week 25

Secondary – Efficacy

- Change from baseline (CFBL) in SNOT-22 total and subdomain scores at Weeks 2, 4, 6, 8, 12, 16, 20, 24, and 28

The SNOT-22 questionnaire is a 22-item disease-specific quality of life instrument validated for use in CRS. Each symptom is scored as it has been over the past 2 weeks on a 6-point scale as follows: 0 = no problem, 1 = very mild problem, 2 = mild or slight problem, 3 = moderate problem, 4 = severe problem, 5 = problem as bad as it can be.

- CFBL in the average composite score over the preceding 7 days of 3 cardinal symptoms (3CS) and individual cardinal symptom scores at Weeks 2, 4, 6, 8, 12, 16, 20, 24, and 28

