Data collected in this study will be presented using listings, as well as summary tables and figures. Continuous data will be summarized by treatment group using the following descriptive statistics: the number of observations (n), mean, standard deviation (SD), median, minimum, and maximum. Categorical data will be summarized by treatment group as number and percentage of subjects in each category. Individual subject's data will be presented in listings.

Subject Disposition and Demographic Characteristics:

Subject disposition will be summarized for all consented subjects. Analysis set assignment will be summarized for all enrolled subjects by treatment group. Demographics and other baseline characteristics and study drug exposure will be summarized for the Efficacy analysis set.

PK Analyses:

The PK analyses will be performed based on subjects with available plasma MF concentration data post Day 1 LYR-220 administration procedure. A summary table will be used to present descriptive statistics (number, mean, SD, coefficient of variation, median, minimum, and maximum) of these PK parameters by treatment group. If plasma MF levels are detectable, PK parameters of MF will be estimated using a standard noncompartmental PK approach based on individual plasma concentration-time data. Maximum concentration (C_{max}) and time to reach maximum concentration (T_{max}) will be taken directly from the observed data. Actual PK sampling times will be used in the derivation of PK parameters. There will be no imputation of missing data.

Safety Analyses:

Safety will be assessed through AEs and changes in laboratory tests, vital signs, nasal endoscopy assessment, IOP and slit-lamp examination using the safety analysis set. AEs will be coded by using the Medical Dictionary for Regulatory Activities (MedDRA) dictionary.

The number and percentage of subjects with incidence of the safety endpoints will be presented by treatment group, where subjects will be classified according to the treatment received. There will be no formal statistical tests comparing treatments on safety endpoints. There will be no imputation of missing data.

Efficacy Analyses:

All efficacy analyses will be carried out after the last subject completes the Week 28 visit or withdraws prematurely prior to Week 28.

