9.6 Safety Analyses

All safety analyses will be performed using the safety analysis set. There will be no formal statistical tests comparing treatments on safety endpoints and there will be no imputation of missing data.

Treatment-emergent adverse events (TEAEs) are defined as AEs that first occurred or worsened in severity after the initiation of study treatment administration.

Adverse events will be coded using the latest version of the Medical Dictionary for Regulatory Activities (MedDRA). For each study treatment, incidence rates (number and percentage of subjects with at least 1 TEAE) will be tabulated by preferred term and system organ class.

TEAEs by maximum severity, TEAEs by highest relationship to study procedure and product, TESAEs, TESAEs leading to death, and TEAEs leading to discontinuation of study treatment will be tabulated as number and percentage of subjects with at least 1 such TEAE for each treatment group overall and by preferred term and system organ class. Note that subjects experiencing >1 event within the same system organ class will be tabulated only under the maximum severity and highest relationship experienced for that system organ class; similarly, subjects experiencing >1 event within the same preferred term will be tabulated only under the maximum severity and highest relationship experienced for that preferred term.

All laboratory test results will be summarized by treatment group using descriptive statistics for actual value and change from baseline. Treatment-emergent abnormal and clinically significantly abnormal laboratory test results, ophthalmology examination findings, and nasal endoscopy findings will be summarized by treatment group.

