# 2.3.2 Secondary Safety Endpoints

The secondary safety endpoints include:

- 1. Treatment-emergent adverse events (TEAEs) and serious adverse events through Week 28/Follow Up.
- 2. Clinically significant abnormal laboratory values (hematology and chemistry) through Week 25/Follow Up.
- 3. Newly identified or worsened endoscopic findings (epistaxis and mucosal injury) in ethmoid cavity through Week 25/Follow Up.
- 4. Clinically significant increase of IOP through Week 25/Follow Up.
- 5. Newly identified or worsened cataract in 1 or both eyes by slit-lamp examination through Week 25/Follow Up.

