#### 3.6.5 Ophthalmologic Assessments

The ophthalmologic assessment of IOP and slit-lamp examination to identify development or worsening of cataract will be conducted at Screening and Week 25/Follow Up visits. The cataract assessment will be conducted according to the Simplified Cataract Grading System authored by the World Health Organization (WHO) Cataract Grading Group. Subject's eyes will be dilated with mydriatics following the WHO guidance for cataract assessment. IOP may be measured using Goldmann applanation tonometer, noncontact tonometer, or tono-pen; however, it is recommended that the same method be used for consistency across serial assessments on a given subject. IOP assessment will also be performed at Week 4 and 12 visits. Assessments will be conducted by an ophthalmologist/optometrist who is blinded to the subject's treatment assignment.

The number and percentage of subjects with clinically significant increase of IOP will be presented by visit and in overall. Descriptive summary statistics on the values and change from base line of IOP will be presented by visit.

The number and percentage of subjects with newly identified or worsened cataract will be presented by visit and in overall.

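### SAP 3.6.2 omits two of the three laboratory summaries specified in protocol 9.6, while SAP Section 5 declares no change

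*SAP*

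**What the plan says.** The protocol synopsis, and the objectives table in protocol Section 3, list this as a secondary safety endpoint: "Clinically significant abnormal laboratory values (hematology and chemistry) through Week 25". SAP 2.3.2 keeps it as the second of five: "Clinically significant abnormal laboratory values (hematology and chemistry) through Week 25/Follow Up".

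On reporting, the synopsis sets a general rule: "The number and percentage of subjects with incidence of the safety endpoints will be presented by treatment group". Protocol 9.6 is more specific about laboratory data. It states "All laboratory test results will be summarized by treatment group using descriptive statistics for actual value and change from baseline", and then "Treatment-emergent abnormal and clinically significantly abnormal laboratory test results, ophthalmology examination findings, and nasal endoscopy findings will be summarized by treatment group".

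SAP 3.6.2 gives the sampling visits and points to an appendix for the list of tests. Its only output sentence is "Descriptive statistics for values will be presented". SAP Section 5 states that the protocol's statistical analyses are unchanged.

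**The concern.** The SAP keeps the endpoint but plans no output built to report it. Change from baseline, which protocol 9.6 names, is also gone. Anyone programming from SAP 3.6.2 would produce summaries of observed laboratory values and stop there.

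The trial's stated purpose is safety, tolerability and pharmacokinetics. Without the missing outputs, the study report could not state directly how many subjects in each group had a clinically significant laboratory abnormality, or how many developed an abnormal result after treatment. Section 5 would also tell readers that nothing had been dropped.

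**Working it through.** No figure in the plan has to be reproduced, so the check is a comparison of text followed by a short count.

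**Step 1. Protocol 9.6 against SAP 3.6.2.**

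| Laboratory output in protocol 9.6 | In SAP 3.6.2? |
|---|---|
| Descriptive statistics, actual value | Yes |
| Descriptive statistics, change from baseline | No |
| By-group summary of treatment-emergent abnormal and clinically significantly abnormal results | No |

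Three are planned and one is kept, so 3 − 1 = 2 are missing. SAP 3.6 says safety data are summarized by treatment received, so the output that remains is at least given by group.

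**Step 2. Can the word values cover change or incidence?** The SAP's own usage says not.
- For intraocular pressure, SAP 3.6.5 names incidence explicitly ("The number and percentage of subjects with clinically significant increase of IOP will be presented by visit and in overall") and, in a separate sentence, names both values and change from baseline.
- SAP 3.6.4 uses the same sentence as 3.6.2 for vital signs. These are measured only at Screening, so there the sentence cannot include change.
- SAP 3.1.4 defines the endoscopy, intraocular pressure and cataract endpoints. It has no laboratory definition.

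**Step 3. The five secondary safety endpoints in SAP 2.3.2.** Adverse events have their own incidence output in SAP 3.6.1, endoscopic findings in 3.6.3, and intraocular pressure and cataract in 3.6.5. Laboratory values have none. That is one of five.

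**Step 4. What reaches the tables by another route?** Protocol 8.3.11.6.1 makes a laboratory result an adverse event if the investigator judges it a clinically significant abnormal change from baseline. SAP 3.6.1 includes such findings in its adverse event definition and tabulates counts and percentages of subjects by system organ class and preferred term. The timing fits: treatment-emergent events run to 31 days after treatment stops, and the Week 25 laboratory window (SAP Table 2a) runs from day 0 to day 31 after treatment. Two gaps remain:
- Events are spread over preferred terms within the Safety Analysis Set. No row collects all subjects with a clinically significant laboratory result, and none uses subjects actually tested as the denominator.
- Abnormal results not judged clinically significant do not become adverse events by this rule, yet protocol 9.6 asks for treatment-emergent abnormal results as well.

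**Step 5. What would one subject weigh?** Part 2 plans about 20 subjects per arm. SAP 3.1 pools LYR-220-32 subjects from both parts for safety. Part 1 has up to 10 subjects and the split by design is not stated, so the LYR-220-32 safety group is about 20 to 30. One affected subject is 1/20 = 5% in the sham group, and between 1/30 = 3.3% and 1/20 = 5% in the LYR-220-32 group. LYR-220-16 is reported as a separate, smaller group.

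**Step 6. Are the data there?** Yes. SAP 3.1.3 gives a baseline rule, Table 2a gives the follow-up window, and the protocol's schedule of assessments has investigators document their review of every laboratory report.

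**The case against.** The best opposing case is that the endpoint is not lost. A reader comparing SAP 2.3.2 with 3.6.2 might infer that it has no analysis at all. The documents do not support that, because of the adverse event route in Step 4. Nor would group means necessarily hide an outlier: descriptive statistics under SAP 3.1.5 include the minimum and maximum, and SAP 3.6 and Section 6 provide subject listings. This part of the objection stands and limits the consequence.

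It does not close the gap. A minimum or maximum does not say how many subjects were affected, whether the investigator judged the value clinically significant, or whether it was new since baseline. A listing is not the by-group summary that protocol 9.6 asks for.

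It can also be said that part of the record is out of view. The SAP contents list an Appendix E on changes from the protocol, whose text is not in the material reviewed, and detailed programming specifications are kept separately. If Appendix E records the reduction, then it is documented. Section 5 would still say the opposite, and SAP 3.6.2 would still lack the outputs.

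Finally, a reader might take protocol 9.6 to require a baseline-to-Week 25 shift table. It does not name one.

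**Conclusion.** The point holds as a mismatch between the two documents. SAP 3.6.2 omits two of the three laboratory summaries in protocol 9.6, Section 5 declares no change, and one of the five secondary safety endpoints has no output of its own. The stronger inference, that this endpoint would go wholly unreported, does not hold.

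The practical loss is a direct by-group number and percentage of tested subjects meeting the endpoint, a by-group summary of treatment-emergent abnormal results, and the change-from-baseline statistics. The primary endpoint is untouched, and no test is affected because the protocol plans no formal safety comparisons. It should be corrected, since the omitted outputs are ones the protocol already promises in a study whose main purpose is safety.

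This assumes that neither Appendix E nor the separate programming specifications restore the missing outputs.

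**What to change.** In SAP 3.6.2 add, by treatment group as pooled in SAP 3.1:
- the number and percentage of subjects with treatment-emergent abnormal hematology or chemistry results through Week 25/Follow Up;
- the number and percentage with clinically significant abnormal results over the same period, with clinical significance taken from the investigator assessment in protocol 8.3.11.6.1;
- descriptive statistics for change from baseline to Week 25.

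State that the denominator for the percentages is subjects with a post-baseline laboratory result. If any of these outputs is deliberately dropped, say so in Section 5. A shift table is an optional way to show treatment-emergent abnormality.

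The cost is a few extra standard tables from data already collected. This is best settled before the primary lock analysis, because SAP 4.2 treats later changes that affect the statistical analysis as post hoc, and these outputs could then carry that label although the protocol had specified them.
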